## **8.0 DEMOGRAPHICS AND OTHER BASELINE DATA**

### **8.1 DEMOGRAPHICS**

Following demographic characteristics will be descriptively summarized for the patients in the Implanted Population.

- Age (years)
- Age group (<60, 60-<70, 70-<80, ≥ 80 years)
- Sex (Male, Female)
- Race (White, Black or African American, Asian, American Indian or Alaska Native, Native Hawaiian or Native Pacific Islander, Multiple)
- Ethnicity (Hispanic or Latino, Not Hispanic or Latino)

### **8.2 BASELINE AND DISEASE CHARACTERISTICS**

Following baseline characteristics will be descriptively summarized for the patients in the Implanted Population (baseline is defined in Section 16.1):

- Study eye (SE) [right (OD), left (OS)]
- Lens status of study eye (phakic, pseudophakic, aphakic)
- Number of prior IOP-lowering medications (0, 1, 2, 3, 4, 5, >5), see Section 8.4.2 for IOP-lowering medication counts.
- Screening and baseline IOP [Hour 0] of SE (mmHg) category (<20, 20-25, >25-30, >30-35, and >35 mmHg) and descriptive summary at baseline
- Best corrected visual acuity (BCVA) of the SE (20/40 or better, <20/40 to 20/100, and worse than 20/100)
- Visual field result of SE (normal, abnormal). Abnormalities will be further broken down by abnormality condition (enlargement of blind spot, superior arcuate scotoma, inferior arcuate scotoma, paracentral scotoma, nasal step, central scotoma, generalized depression, temporal scotoma, other)
- Visual field mean deviation (dB) or mean defect of the SE (+, -)
- Ophthalmoscopy, cup to disc ratio of SE at baseline
- Contact Pachymetry at screening: central corneal thickness mean (µm) of the SE, and a categorical summary (<500, 500-<525, 525-<550, 550-<575, 575-<600 and ≥600 µm)

In addition, following medical history data collected on the ‘Medical and Surgical History/Physical Findings’ eCRF page will also be summarized.

- History of trabeculectomy or glaucoma shunt implantation (yes, no)
- History of trabeculectomy (yes, no)
- History of glaucoma shunt implantation (yes, no)
- Prior Cataract Surgery (yes, no)
- Prior Glaucoma Procedure (yes, no).
  - Yes, with incisional or cilioablative procedure
  - Yes, without incisional or cilioablative procedure

A look-up table of Medical Dictionary for Regulatory Activities (MedDRA) terms to identify the following procedures will be provided by the study medical safety physician (MSP):

- Trabeculectomy
- Glaucoma shunt implantation
- Cataract Surgery
- Glaucoma Procedure
  - Incisional or cilioablative procedure
  - Not incisional or cilioablative procedure

### **8.3 MEDICAL HISTORY**

Medical and surgical histories will be coded using the MedDRA, version 24.0 or newer. The number and percentage of patients with non-ocular medical and surgical histories will be summarized by system organ class and preferred term in the Implanted Population. Ocular medical and surgical histories will be summarized by study and fellow eye, system organ class and preferred term in the Implanted Population.

Medical and surgical histories will also be listed for patients in the Implanted Population.

### **8.4 PRIOR AND CONCOMITANT MEDICATIONS**

Medications will be coded using the current version of World Health Organization (WHO) Drug Dictionary and anatomical therapeutic chemical classification system and patient incidences will be summarized by therapeutic class and preferred drug name for patients in the Implanted Population. If a patient took a specific medication multiple times or took multiple medications within a specific therapeutic class, that patient will be counted only once for the coded drug name or therapeutic class.

Prior medications are defined as medications taken before the date of XEN implantation. Concomitant medications are defined as those medications taken on or after the date of XEN implantation.

Prior and concomitant medications will also be listed for patients in the Implanted Population.

#### **8.4.1 General Medications**

Prior and concomitant medications discussed in this section do not include medications of interest collected on the ‘IOP meds’ and ‘IOP meds other’ eCRF pages.

Non-ocular medications will be summarized separately for:

- Prior medications
- Concomitant medication

Ocular medications will be summarized by study and fellow eye separately for:

- Prior medications
- Concomitant medications

#### **8.4.2 IOP-lowering Medications**

IOP-lowering medications collected on the ‘IOP meds’ and ‘IOP meds other’ eCRF pages will be summarized by study and fellow eye separately for:

- Prior medications
- Concomitant medications

In addition, the number of IOP-lowering medications is one of the secondary effectiveness endpoint (analysis is described in Section 10.2). Fixed-combination medications will be counted as multiple medications, including but not limited to Azarga, Combigan, Cosopt, Duotrav, Ganfort, Simbrinza, and Xalacom, which will be counted as 2 medications. A list of these medications will be confirmed by clinical team prior to database lock.

### **9.0 EXTENT OF EXPOSURE AND TREATMENT COMPLIANCE**

XEN may be removed if the investigator believes that it is in the best interest of the patient. Time to XEN device explant will be summarized by Kaplan-Meier (K-M) analysis.

### **10.0 EFFECTIVENESS ANALYSES**

The primary effectiveness measure is based on IOP measurements at post-baseline visits and number of IOP-lowering medications taken during post-baseline visits (see section 16.1 for more details). Any IOP measurements collected following non-study surgical procedures for IOP control or device explant (i.e., device failures) will be excluded from the analyses. Any medications taken following non-study surgical procedures for IOP

control will be excluded when determining the number of IOP-lowering medications. A look-up table of MedDRA terms to identify non-study surgical procedures for IOP control will be provided by the study MSP.

No formal statistical hypothesis will be tested.

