8.2 Collection/Derivation of Primary and Secondary Effectiveness Assessments

The primary effectiveness measure, IOP, will be measured using a Goldmann applanation tonometer. The measurements will be collected using the masked examiner method described in the Protocol Procedure Manual. Additionally, the number of concomitant IOP-lowering medications following implantation will be recorded. To determine the number of concomitant IOP-lowering medications, fixed-combination medications will be counted as multiple medications. For example, Combigan will be counted as 2 medications. Any IOP measurements or medication counts collected following non-study surgical procedures for IOP control or device explant (ie, device failures) will be excluded from the analyses.

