## 10.2 SECONDARY EFFECTIVENESS ASSESSMENTS

The mean and 2-sided 95% CI for raw Hour 0 IOP and the corresponding change from baseline Hour 0 IOP will be estimated using mixed-effects model for repeat measures (MMRM) at Month 1, 3, 6, 8, 10, and 12 with visit as a fixed effect and baseline Hour 0 IOP as a covariate. An unstructured covariance matrix will be used for repeated measures on the same patient; if the model with unstructured covariance fails to converge, an alternative covariance structure will be chosen. MIXED procedure available in SAS software will be used to fit the MMRM model; see sample SAS code below:

[figure not shown]
```
proc mixed data=one(where=(visit gt 0)) method=reml;  
  class visit pid;  
  model respvar=bliop visit/ddfm=kr;  
  repeated visit/subject=pid type=un;  
  lsmeans visit/cl alpha=0.05;  
  ods output lsmeans=lsms(keep=visit estimate lower upper);  
run;
```

The variable ‘respvar’ represents the Hour 0 IOP or corresponding change from baseline as applicable. Other variables are same as those described in Section 10.1. The least squares means and 95% CIs for Months 1, 3, 6, 8, 10 and 12 will be tabulated. In fitting the above model, missing data will not be imputed.

[figure not shown]
The number of IOP-lowering medications taken and corresponding change from baseline will be summarized by visit with descriptive statistics and 2-sided 95% CI for the mean. The change from baseline in the number of IOP-lowering medications taken will also be summarized by visit and the following categories:  $\geq 3$  medications reductions, 2 medications reductions, 1 medication reduction, no change, 1 medication increase, 2 medications increase, and  $\geq 3$  medications increase.

Mean (SE) Hour 0 IOP will be plotted overtime without missing data imputation and mean number of IOP-lowering medications taken will be displayed by visit in the plot.

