### **16.0 DATA HANDLING CONVENTIONS**

#### **16.1 VISIT TIME WINDOWS**

Table 16.1–1 presents the analysis visits assigned for efficacy and safety analyses and the corresponding range in Study days (window) during which an actual visit may occur.

Table 16.1–1. Visit Time Windows

Analysis Visit	Target Visit Daya	Window
Baseline	Day 1	Days $\leq 1$
Day 2	Day 2	Days [2, 4]
Day 8	Day 8	Days [5, 11]
Week 2	Day 15	Days [12, 22]
Month 1	Day 31	Days [23, 61]
Month 3	Day 92	Days [62, 137]

Month 6	Day 183	Days [138, 213]
Month 8	Day 244	Days [214, 274]
Month 10	Day 305	Days [275, 335]
Month 12	Day 366	Days $\geq$ 336

a Relative to the date of the XEN implant. Day 1 = the date of the XEN implant. There is no Day 0 or Week 0.

If an assessment date (if the assessment date is unavailable, use visit date instead) is on or after the date of XEN implant, the study day is calculated using (Assessment date – date of the XEN implant + 1). If the assessment date is before the date of the XEN implant, the study day is calculated using (Assessment date – date of XEN implant). Therefore, a negative day indicates a day prior to XEN implant date.

For multiple scheduled or unscheduled visits falling within the same analysis visit window, the assessment closest to the target visit day will be used for by visit summaries. If two visits are equally close to the target visit day, the later visit will be used as analysis visit.

For by visit and severity summaries, the results with maximum severity for the visit should be chosen if multiple scheduled or unscheduled visits falling within the same analysis visit window.

For number of IOP-lowering medications taken during post-baseline visits, analysis visits for IOP measurements will be derived first. Post-baseline analysis visit days of IOP measurements will then be compared to start and stop date of each concomitant IOP-lowering medication record to determine number of IOP-lowering medications taken during post-baseline visits.

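### After non-study IOP surgery the SAP removes the drugs rather than the count, so a device failure can be tabulated as drug-free in the secondary medication summaries

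*SAP*

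**What the plan says.** Protocol 8.2 has one rule for both kinds of data. It covers "Any IOP measurements or medication counts collected following non-study surgical procedures for IOP control or device explant" and takes them out of the analyses. The thing removed is the count, and both surgery and explant trigger the removal.

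SAP 10.0 splits this rule in two.

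- For pressure it keeps the protocol's rule: "Any IOP measurements collected following non-study surgical procedures for IOP control or device explant (i.e., device failures) will be excluded from the analyses".
- For drugs the wording changes: "Any medications taken following non-study surgical procedures for IOP" "control will be excluded when determining the number of IOP-lowering medications" (one sentence, quoted in two parts). The thing removed is now the drug, and explant is not named.

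SAP 16.1 explains how a count is built. For this purpose "analysis visits for IOP measurements will be derived first", and then "Post-baseline analysis visit days of IOP measurements will then be compared to start and stop date of each concomitant IOP-lowering medication record".

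SAP 10.2 uses the result: "The number of IOP-lowering medications taken and corresponding change from baseline will be summarized by visit", with a 95% CI for the mean and a table of change categories whose top level is a reduction of three or more drugs.

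SAP 17.0 declares a single departure from the protocol, which is that secondary endpoints get no sensitivity analyses. The changed medication rule is not listed.

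**The concern.** If every drug taken after surgery is left out when the number is worked out, the number is 0. That differs from having no number. Under the protocol such a visit contributes nothing to the medication summaries. Under the literal SAP wording it contributes the best possible value.

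The eyes concerned are ones that both documents call device failures. An eye with three or more drugs at baseline that is coded 0 lands in the most favourable change category, whatever the patient is actually taking. A wrong zero can only make the medication result look better. No sensitivity analysis of this endpoint would show it, because SAP 17.0 rules those out.

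Such eyes can exist. Protocol 6.5 makes withdrawal after implantation mandatory only for device removal or a suture closing the scleral channel. Protocol 4.4.2 prohibits other glaucoma surgery in the study eye, but a patient who has it and keeps the device is not on the mandatory withdrawal list. Protocol 8.2 itself expects data to be collected after such surgery.

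**Working it through.** **The plan's own figure.** The plan gives no figure for this point. Its one precision statement (SAP 14.0: 50 patients, ±0.145, exact Clopper-Pearson) concerns the responder proportion. It reproduces: the widest interval is at 25 of 50, from 0.3553 to 0.6447, half-width (0.6447 − 0.3553)/2 = 0.1447. Nothing below depends on it.

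**Step 1. The two rules side by side, for a visit after the event.**

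| Event | Protocol 8.2 | SAP 10.0, read literally |
|---|---|---|
| Non-study IOP surgery, device kept | count excluded | drugs excluded, so count = 0 if the visit is counted |
| Device explant | count excluded | no medication rule, so the actual count is kept |

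**Step 2. Does the visit receive a count?** SAP 16.1 counts drugs only on IOP analysis visit days. Two orders of work fit the text:

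- Visits derived first, post-surgery IOP dropped from the analyses afterwards: the visit day exists, its drugs are left out, and the count is 0.
- Post-surgery IOP dropped before visits are derived: there is no visit day, and the count is missing, as in the protocol.

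The SAP does not state the order.

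**Step 3. Effect on the primary endpoint.** A responder needs both an IOP reduction of at least 20% and no more drugs than at baseline (SAP 10.1.1). Post-surgery IOP is excluded and not imputed in the primary model, so a count of 0 cannot create a responder. In the sensitivity analysis (SAP 10.1.2) post-surgery IOP is imputed by worst observation carried forward. A 0 is not missing, so it escapes the same rule for missing counts and meets the drug half of the definition. The carried-forward IOP must still show the 20% reduction.

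**Step 4. Illustration for the secondary endpoint.** The inputs come from the earlier US trial in Protocol 2.1: baseline mean 3.5 drugs (N = 65); Month 12 mean 1.7, SD 1.5 (n = 52); 13.8% with secondary surgery, and 0.138 × 65 = 8.97, about 9 patients. Assumptions: the 52 contain none of the affected eyes, the baseline mean is 3.5 in both groups, and f affected eyes reach Month 12 and are coded 0.

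- Mean count = 52 × 1.7 / (52 + f) = 88.4 / (52 + f)
- Mean change = (52 × (−1.8) + f × (−3.5)) / (52 + f), where −1.8 = 1.7 − 3.5

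| f | Mean count | Mean change |
|---|---|---|
| 0 (protocol rule) | 1.70 | −1.80 |
| 1 | 88.4/53 = 1.67 | −97.1/53 = −1.83 |
| 3 | 88.4/55 = 1.61 | −104.1/55 = −1.89 |
| 9 | 88.4/61 = 1.45 | −125.1/61 = −2.05 |

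For scale, the t-based 95% CI for the mean with f = 0 is 1.28 to 2.12, a half-width of 0.42.

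**The case against.** A reader might infer that these eyes do enter the medication tables as drug-free. The documents do not establish that. SAP 16.1 ties counts to IOP analysis visit days, and the sentence just before the medication rule in SAP 10.0 removes post-surgery IOP. If that removal comes first, the count is missing. Some context supports this benign reading: SAP 4.0 presents the SAP as an elaboration of the protocol, and SAP 10.1.2 provides for missing counts. The latter is not decisive, since counts can also be missing through loss to follow-up. Against the benign reading, the medication sentence affects a post-surgery visit only if that visit still receives a count; otherwise it has nothing to do there. So the point stands as an ambiguity: two competent programmers could produce different tables.

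A reader might also infer that the primary result is inflated. Step 3 shows that it is not in the main model, and that in the sensitivity analysis the carried-forward IOP still has to qualify.

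The affected group may be small. Protocol 6.1.3.2.3 gives trabeculectomy as its example of surgery requiring explant, and explanted patients are withdrawn. That section says only that removal may be considered, so a retained device remains possible, but the documents give no rate for it. For the same reason the omission of explant matters little: at most an early-exit visit after explant would carry the patient's real count, not a zero.

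Finally, the endpoint is descriptive, SAP 10.0 tests no hypothesis, and even nine affected eyes move the mean by 0.25, inside the illustrative half-width of 0.42. This limits the size of the problem but does not remove the undeclared conflict or its one-sided direction.

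**Conclusion.** The concern holds as a conflict between the documents with a possible consequence. The SAP changes the protocol's exclusion from counts to drugs, leaves out explant, and declares neither change. Taken literally, its rule lets a device failure be tabulated at zero drugs in a secondary endpoint, and a wrong zero there can only favour the device. Whether it happens turns on a programming order that the SAP does not give.

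The likely size is small. In the illustration one to three such eyes shift the Month 12 mean by 0.03 to 0.09 drugs. The 0.25 shift with nine is an upper bound: it takes every secondary surgery in a different trial, in refractory glaucoma, to be IOP surgery with the device kept, with all of those patients followed to Month 12 and none among the 52. The number of such eyes in this trial is an assumption throughout.

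**What to change.** Replace the medication sentence in SAP 10.0 with the protocol's rule: at any visit after a non-study operation to control IOP, or after explant, the IOP-lowering medication count is set to missing in the by-visit summaries and change categories. The existing worst-observation rule for missing counts then applies to these visits in the sensitivity analysis of the primary endpoint. Under each by-visit medication table, report how many eyes were set to missing for this reason.

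The cost is one SAP sentence, a programming flag and a table footnote. No new method or data collection is needed. The reported reduction in drugs may be slightly smaller than under the zero coding.

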## **10.1 PRIMARY EFFECTIVENESS ASSESSMENTS**

### **10.1.1 Primary Analysis**

The primary effectiveness analysis will estimate the proportion of patients, with corresponding 2-sided 95% CI, that achieve at least a 20% reduction from baseline Hour 0 IOP while on the same number or fewer IOP-lowering medications at Month 12 compared with baseline using a mixed-effects repeated measures logistic regression model. The model will include visit as a fixed effect and baseline IOP as a covariate for repeated measures at Month 1, 3, 6, 8, 10, and 12. An unstructured covariance matrix will be used for repeated measures on the same patient; if the model with unstructured covariance fails to converge, an alternative covariance structure will be chosen. The Hour 0 IOP percent change from baseline at a timepoint is calculated as:

$$100 \times (\text{Timepoint Hour 0 IOP} - \text{Baseline Hour 0 IOP}) / \text{Baseline Hour 0 IOP}$$

First, a response variable will be derived from the effectiveness variables: Hour 0 IOP percent change from baseline and the number of concomitant IOP-lowering medications. If the percent change in Hour 0 IOP from baseline is less than or equal to  $-20\%$  at an analysis timepoint of interest **and** the number of IOP-lowering medications taken at the that timepoint is same or fewer compared to that at baseline, the response variable will be coded to value 1 and 0 otherwise. Refer to Section 8.4.2 for a discussion on determining the number of IOP-lowering medications taken at a timepoint of interest. GENMOD procedure available in SAS software will be used to fit the repeated measures logistic regression model; see sample SAS code below:

```
proc genmod data=one(where=(visit gt 0)) descending;
  class visit pid;
  model resp=bliop visit/link=logit dist=bin;
  repeated subject=pid/type=un within=visit;
  lsmeans visit/cl alpha=0.05;
  ods output lsmeans=lsms(keep=visit estimate lower upper);
run;
```

The variable ‘resp’ denotes the derived response variable as described above; ‘visit’ denotes the analysis visit month with the value 0 representing baseline; ‘pid’ is the unique patient ID; ‘bliop’ is the baseline Hour 0 IOP. Required proportion and 95% CIs at each assessment visit will be obtained by respectively applying the inverse logit transformation,  $\exp(\cdot)/(1+\exp(\cdot))$ , to ‘estimate’, ‘lower’ and ‘upper’ values contained in output dataset ‘lsms’ created by the ‘ods output’ statement. The proportion estimates and 95% CIs for Month 1, 3, 6, 8, 10 and 12 will be tabulated. In fitting the above model, missing data will not be imputed.

For Baseline and Month 12/Exit visits, Hour 0 IOP data from Hour 0 IOP eCRF page will be used. For all other visits without diurnal IOP assessment, all IOP collected for efficacy will be used.

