8.2.1 Primary Effectiveness Variable

The primary effectiveness endpoint is the proportion of patients achieving at least a 20% reduction from baseline Hour 0 IOP while on the same number or fewer IOP-lowering medications at Month 12 and is derived from the effectiveness variables: Hour 0 IOP percent change from baseline and the number of concomitant IOP-lowering medications. The Hour 0 IOP percent change from baseline is calculated as $100 * (\text{Hour 0 IOP change from baseline}) / \text{baseline Hour 0 IOP}$.

The number of concomitant IOP-lowering medications following implantation will be compared with the number prior to implantation.

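### The Month 12 figure labelled as the proportion of patients is the modelled response probability at mean baseline IOP, and it will usually run slightly high

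*SAP*

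**What the plan says.** Protocol 8.2.1 defines the target: "The primary effectiveness endpoint is the proportion of patients achieving at least a 20% reduction from baseline Hour 0 IOP", combined with a medication count no higher than at baseline, at Month 12. SAP 10.1.1 repeats that target: "The primary effectiveness analysis will estimate the proportion of patients, with corresponding 2-sided 95% CI".

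The sample code in SAP 10.1.1 contains three relevant lines:

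- the model, "model resp=bliop visit/link=logit dist=bin";
- the repeated-measures statement, "repeated subject=pid/type=un within=visit", which makes this a generalised estimating equation (GEE) fit, that is, a population-averaged model;
- the estimates, "lsmeans visit/cl alpha=0.05", with no option that changes the covariate value or averages over patients.

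The SAP then specifies: "Required proportion and 95% CIs at each assessment visit will be obtained by respectively applying the inverse logit transformation". The text describes the analysis as "using a mixed-effects repeated measures logistic regression model", which does not match the population-averaged code.

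SAP 10.0 adds: "No formal statistical hypothesis will be tested". SAP 10.1.2 plans a descriptive observed-data summary of the same endpoint, and a multiple-imputation analysis that reuses the same model and least-squares means.

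**The concern.** The inverse logit is not linear. Transforming the average linear predictor gives a different number from averaging the transformed predictors. The planned figure answers how likely response is for a patient with average baseline IOP. The protocol asks what share of patients respond.

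A dependence on baseline is likely because of how response is defined. To pass, Month 12 IOP must be at most 0.8 times baseline, so each extra mm Hg at baseline raises the passing limit by 0.8 mm Hg. On the IOP part of the endpoint, the baseline effect vanishes only if post-operative IOP itself rises by about 0.8 mm Hg per mm Hg of baseline.

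The SAP calls this single-arm study pivotal, and its main result is this one estimate. The discrepancy does not shrink as the sample grows.

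**Working it through.** **The plan's own figure.** For n = 50, the widest exact Clopper-Pearson 95% interval occurs at 25/50, with a half-width of 0.1447. This reproduces the stated ±0.145. At 38/50 = 76% the interval is 0.618 to 0.869, so the half-width is (0.869 − 0.618)/2 = 0.126.

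**Inputs from the documents.** Protocol 2.1 reports, for the earlier US study in refractory glaucoma, a Month 12 response of 76%, baseline IOP of 25.1 (SD 3.7) mm Hg, and a mean IOP reduction with SEM 1.1. Inclusion criterion 6 limits baseline IOP to 20–35 mm Hg. I assume the 76% and the baseline spread carry over to this trial. A normal distribution (25.1, 3.7) truncated to 20–35 has mean 25.7 and SD 3.1. The slope of response on baseline is not in the documents, so it is shown as a range.

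**Step 1: gap for a given slope.** Let x be baseline IOP, x̄ its mean, b the log-odds slope per mm Hg, and expit the inverse logit.

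- Marginal proportion = average of expit(a + b(x − x̄)) over patients.
- SAP figure = expit(a).

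Solve for a so that the marginal proportion is 0.76. For b = 0.2, a = 1.250 and expit(1.250) = 77.7%, a gap of 1.7 points.

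| Slope b | Odds ratio per 5 mm Hg | SAP figure when the truth is 76% |
|---|---|---|
| 0 | 1.0 | 76.0% |
| 0.05 | 1.3 | 76.1% |
| 0.1 | 1.65 | 76.5% |
| 0.2 | 2.7 | 77.7% |
| 0.3 | 4.5 | 79.6% |

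A baseline spread uniform over 20–35 (SD 4.3), wider than in the reference study, gives gaps of 0.9, 3.2 and 6.5 points at b = 0.1, 0.2 and 0.3.

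**Step 2: what slope does the endpoint imply?** Let post-operative IOP be normal with mean m + d(x − x̄) and SD s, and let a share q meet the medication condition regardless of baseline. Then

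P(response | x) = q · Φ((0.8x − m − d(x − x̄))/s).

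Choose m so that this averages 0.76, fit a logistic regression on x, and compare the fit at x̄ with 76%. For s = 4, d = 0, q = 1: m = 17.2, slope 0.35, fitted value 80.7%. For s = 7: m = 15.3, slope 0.20, fitted value 77.7%. Gaps in points:

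| | s = 4 | s = 5 | s = 7 | s = 8 |
|---|---|---|---|---|
| q = 1, d = 0 | 4.7 | 3.2 | 1.7 | 1.3 |
| q = 1, d = 0.3 | 2.0 | 1.3 | 0.7 | 0.5 |
| q = 1, d = 0.6 | 0.3 | 0.2 | 0.1 | 0.1 |
| q = 0.92, d = 0 | 2.3 | 1.6 | 0.9 | 0.7 |
| q = 0.92, d = 0.3 | 1.1 | 0.7 | 0.4 | 0.3 |
| q = 0.92, d = 0.6 | 0.2 | 0.1 | 0.1 | 0.05 |

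The values of d and q are assumptions.

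**Step 3: which s is plausible?** Read the SEM as SD/√n. The SD of the IOP change is then 1.1 × √52 = 7.9 or 1.1 × √65 = 8.9 (which n applies is not stated). If post-operative IOP is unrelated to baseline, s = √(7.9² − 3.7²) = 7.0 or √(8.9² − 3.7²) = 8.1. At s of 7 to 8 with d from 0 to 0.3, the gap is 0.5 to 1.7 points even when q = 1.

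**Step 4: effect on the interval.** In simulations with 50 patients, six visits and 300 replicates per setting (exchangeable working correlation), the SAP figure exceeded the crude rate at a true 76% by 0.25, 0.71 and 1.88 points on average for slopes 0, 0.1 and 0.2. Over nine settings with slopes up to 0.2, coverage of the marginal rate was 93% to 97%.

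**The case against.** A reader might infer that the result is systematically inflated whenever it exceeds 50%. That goes too far. With no baseline effect the gap is zero. With a right-skewed baseline and a negative slope it can reverse just above 50%: a true 52% becomes 51.6% at slope −0.2 and 50.8% at −0.3.

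A reader might also take the 5-point figure as typical. It requires a post-operative SD of about 4, no dependence on baseline and no medication failures. The reference study's SEM points to an SD nearer 7 to 8. Protocol 4.4.1.1 lets investigators add IOP-lowering drugs when IOP is off target, so some failures on medication count are to be expected.

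The consequence is limited. No hypothesis or performance goal depends on the number, sampling error is several times larger, and interval coverage held up in the settings simulated.

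SAP 10.1.2 already plans the crude observed proportion, which would show the gap if data were complete. This safeguard is only partial. The design allows 15 of 65 patients (23.1%) without 12 months of follow-up, and a difference between the crude and modelled rates could then come from missing visits instead.

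It is also tempting to say that baseline IOP serves no purpose in a single-arm model and should be dropped. The documents do not support that. Protocol 8.3.1 specifies the covariate, and because the primary model does not impute, conditioning on baseline IOP lets missingness depend on it.

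**Conclusion.** The mismatch between label and estimate follows from the SAP's text and code, together with the software's default for least-squares means. Its direction is usually upward when the true rate is well above 50%. Its size is a matter of assumption: with a true 76% and the reference study's baseline spread, about 0 to 2 points in plausible settings and close to 5 points at the extreme. A wider baseline spread combined with a steep slope would add to this. All of these should be set against about 12.6 points of sampling half-width. This is a modest, avoidable error in the main estimate and does not invalidate the analysis.

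The description as mixed-effects matters more than it may appear. If a random-intercept model were fitted and its intercept-level value back-transformed, a true 76% would be reported as 79.9% with a random-intercept SD of 1, and as 86.6% with an SD of 2. The SAP's code does not fit that model, but its wording would permit someone to do so.

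**What to change.** - In SAP 10.1.1, keep the pre-specified GEE with visit and baseline IOP. Report the Month 12 proportion as the average of the predicted Month 12 probabilities over all implanted patients, each at their own baseline IOP, with a delta-method or patient-level bootstrap 95% CI. Do the same for the other tabulated visits.
- In SAP 10.1.2, compute the same averaged proportion and its standard error within each imputation. The combining step there already expects a proportion and a standard error.
- Replace the mixed-effects description with population-averaged (GEE) logistic regression, to match the GENMOD code.
- Do not remove baseline IOP from the model.

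If nothing else is changed, the tables should at least state that the estimate is conditional on mean baseline IOP.

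The cost is a wording change and a few lines of code, with no new data. The reported proportion will usually be slightly lower.
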